643 B) The precision estimated here is the median precision. Precision will vary as a function of the observed
644 standard deviation (as well as sample size), and in any single study will be narrower or wider than this
645 estimate.

Mean(1)= 6.000. Mean(2)= 6.700. Common SD = 1.000

646

647 10 Quality Control and Quality Assurance

648 10.1 Monitoring

649 During the course of the trial, the Monitor will visit the trial site to ensure that the protocol has
650 been adhered to, that all issues have been recorded, perform source data verification, monitor
651 drug accountability etc. The study will be monitored by a boarded monitor ([name],
652 Metabolab Södersjukhuset). All adverse effects regardless of relationship to study drug or
653 protocol procedure will be recorded in the adverse event CRF.

654 The monitor must be given direct access to source documents (original documents, data and
655 records). Direct access includes permission to examine, analyse, verify and reproduce any
656 record(s) and report(s) that are important to the evaluation of the clinical trial. In order to that, a
657 written consent from patient should be fulfilled. In addition the monitor should be available for
658 discussions by telephone.

659 An investigator Source Document Verification Agreement will be completed and signed for each
660 site in order to describe where source data for each data item can be found.

661 The monitor will ensure that the CRFs are completed by site staff.

662 11 Ethics

663 11.1 Ethical Conduct of the Trial

664 The protocol will be reviewed and approved by an IEC. The trial will be performed in
665 accordance with the protocol guidelines in full accordance with Good Clinical Practice and
666 applicable local regulatory requirements and laws. The investigator must insure that each trial

Protocol No: *EudraCT nr 2010022695-31*

Date: *20110204*

Version: *7.5*

667 subject is fully informed about the nature and the objectives of the trial and possible risks
668 associated with participation. The investigator will obtain written informed consent from each
669 subject before any trial-specific activity is performed. The investigator will retain the original of
670 each subject's signed consent form.

671 **11.2 Subject Information and Informed Consent**

672 In obtaining and documenting informed consent, the Investigator must comply with applicable
673 regulatory requirement and adhere to the ICH GCP and the requirements in the Declaration of the
674 Helsinki

675 Prior to any trial related activity, the Investigator must give the subject oral and written
676 information about the trial in a form that the subject can read and understand.

677 A voluntary, signed and personally dated, including time, informed consent must be obtained
678 from the subject before any trial related activity. The subject must be provided with a copy of
679 his/her signed informed consent.

680 The responsibility for obtaining informed consent must remain with that of a medically qualified
681 person and cannot be delegated to a non-medical qualified person. The written informed consent
682 must be signed and personally dated, by the person who obtained the informed consent.

683 If information becomes available that may be relevant to the subject's willingness to continue
684 participating in the trial, the Investigator must inform the subject in a timely manner, and a
685 revised written informed consent must be obtained.

686 Once a subject's participation in the trial has ended no additional care different from what is
687 normally provided according to subjects medical condition is required.

688 **12 Data Handling and Record Keeping**

689 **12.1 Case Report Forms**

690 A case report form (CRF) will be obtained and completed for each included patient. Investigators
691 will ensure completion and review of the CRF. Investigators have personal responsibility for the
692 accuracy and authenticity of all clinical and laboratory data that are entered into the CRF. CRFs,
693 including paper charts, will be stored in locked and secure place. However, in case of emergency,
694 CRFs will be made readily available.

695 **13 Financing and Insurance**

696 Separate financially protocol will be set up. Subjects are insured accordingly to the Swedish
697 patient insurance scheme and the Swedish Drug Insurance Scheme.

698 **14 Publication Policy**

699 The results of the trial will be published by the investigators in an international scientific journal.

Protocol No: EudraCT nr 2010022695-31

Date: 20110204

Version: 7.5

700 **15 Supplements**

701 **15.1 Amendments**

702 Before the Investigator starts the trial, the following documents must be available:

- 703 • Regulatory approval and/or notification as required (independent ethics committee and
704 the Medical Products Agency – Sweden)

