51	15.2	PERSONNEL INFORMATION.....	27
52	16	REFERENCES	28
53	17	APPENDICES.....	30

Protocol No: EudraCT nr 2010022695-31

Date: 20110204

Version: 7.5

54	17.1	SCHEDULE OF INVESTIGATIONAL EVENTS.....	30
55	17.2	SPC GLIMEPIRIDE	30
56	17.3	SPC LIRAGLUTIDE	30
57			

58 Protocol Summary

PROTOCOL IDENTITY AND OBJECTIVES

EudraCT Number:	2010022695-31
Protocol Title:	Effects on subclinical heart failure in type 2 diabetic subjects on liraglutide treatment versus glimepiride both in combination with metformin
Trial Objectives:	To investigate whether liraglutide 1.8 mg QD improves left ventricle longitudinal functional reserve. An 18 week, open, assessor-blinded and active-controlled, parallel-group trial.

INVESTIGATIONAL MEDICINAL PRODUCTS (IMP)

Test Product:	Liraglutide
Pharmaceutical Form:	Solution for injection in prefilled pen
Route of Administration:	Subcutaneous (s.c)
Test Product:	Glimepiride
Pharmaceutical Form:	Tablet
Route of Administration:	Oral (p.o)

METHODOLOGY

Trial Design:	Open, assessor-blinded and active-controlled, parallel-group trial, in combination with metformin
Dose/Duration:	1.8 mg liraglutide QD vs. glimepiride 4 mg QD in total 18 weeks
Primary Endpoint:	Increase in left ventricle longitudinal function and/or functional reserve during rest and after exercise
Efficacy Parameters:	Improvement in left ventricle longitudinal functional reserve, as measured by tissue Doppler echocardiography
Safety Parameters:	

POPULATION OF TRIAL SUBJECTS

Description of Trial Subjects:	Type 2 diabetes subjects with an HbA1c above 60 mmol/mol
Number of Subjects:	Eighty (80)

TRIAL TIMETABLE

First Subject In:	2011
Last Subject In:	2011
Last Subject Out:	2012

59

Protocol No: *EudraCT nr 2010022695-31*

Date: *20110204*

Version: *7.5*

5(30)

60 Abbreviations

Abbreviation	Explanation
AE	Adverse Event
ADR	Adverse Drug Reaction
CRF	Case Report Form
IB	Investigator's Brochure
ICH	International Conference of Harmonisation
IEC	Independent Ethics Committee
IMP	Investigational Medicinal Products
MPA	Medicinal Product Agency
SADR	Serious Adverse Drug Reaction
SAE	Serious Adverse Event
SPC	Summary of Product Characteristics
SUSAR	Suspected Unexpected Serious Adverse Reaction

61

62 **1 Administrative Information**

63 [name]

64 Karolinska Institutet, Department of Clinical Science and Education Division of Internal

65 Medicine Södersjukhuset AB, Stockholm, Sweden.

66 [name]

67

68 [name]

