117 activation of GLP-1 signalling has been shown to influence *e.g.* heart rate and blood pressure [6].
118 In a knock-out mouse model, GLP-1R^{-/-} mice exhibited a defective cardiovascular contractile
119 response together with left ventricular hypertrophy [7]. GLP-1 improves severe left ventricular
120 heart failure in humans suffering from a myocardial infarction [8]. Hence, it has been
121 demonstrated that GLP-1 exerts direct functional effects through both GLP-1 receptor dependent
122 and independent pathways in the heart [9].

123 Native GLP-1 is an extremely short acting peptide, with a half-time breakdown of 1-2 minutes, a
124 feature that makes it unsuitable as a drug treatment for type 2 diabetes. To this end, several long-
125 acting GLP-1 analogues, drugs for treating type 2 diabetes, have been tested for this purpose. The
126 analogue liraglutide exerts its effects via the native GLP-1 receptor, localized not only on the
127 pancreatic β -cells, but also in the human heart. Interestingly, liraglutide has been demonstrated to
128 have beneficial effect on heart function in mice [10]. Taken together, recent data shows that
129 GLP-1 and its stable analogue liraglutide exert beneficial cardiovascular effects.

130 2.1 Trial Rationale

131 Acutely beneficial cardiovascular effects of GLP-1 on the heart have recently been demonstrated.
132 Therefore the rationale for this study is to investigate liraglutide effect on the heart in type 2
133 diabetic subjects. The 18 week treatment period is expected to be sufficient to evaluate the
134 efficacy and safety of the treatment to be studied. Also, the comparator was chosen due to the
135 fact that glimepiride 4 mg QD has an equal anti-diabetic effects in terms of lowering plasma
136 glucose as for liraglutide 1.8 mg QD, during a 18 week period [11]. In order to obtain the
137 necessary power in the trial, 80 subjects are expected to complete the trial (further described
138 under Determination of sample size, section 9.2).

139

Protocol No: EudraCT nr 2010022695-31

Date: 20110204

Version: 7.5

9(30)

140 3 Endpoints

141 3.1 Primary Endpoints

142 Subjects achieving an absolute increase in left ventricle longitudinal function and/or functional
143 reserve during rest and/or after exercise of 0.7 cm/s, i.e., $\Delta E' [1-(1/E'_{base})]$ or $\Delta S' [1-(1/S'_{base})]$
144 after 18 weeks of liraglutide + metformin, compared with glimepiride + metformin, using tissue
145 Doppler echocardiography.

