617 If an SAE occurs in relation to a pregnancy, either to the mother or the newborn, then follow the
618 same reporting requirements and timelines as for SAE.

619 **9 Statistics and Data Management**

[figure not shown]
620 **9.1 Data Management**

621 A case report form (CRF) will be obtained and completed for each included patient. Investigators
 622 will ensure completion and review of the CRF. Investigators have personal responsibility for the
 623 accuracy and authenticity of all clinical and laboratory data that are entered into the CRF. Also,
 624 electronic charts will be transferred to paper charts and stored for each included patient. CRFs,
 625 including paper charts, will be in locked in a safe place. However, in case of emergency, CRFs
 626 will be made readily available.

627 **9.2 Determination of Sample Size**

628 The primary endpoint is defined as an improvement of LV longitudinal contraction measured
 629 with tissue Doppler echocardiography at rest and at ECG Stress Test. Longitudinal diastolic
 630 function reserve index = $\Delta E' [1 - (1/ E'_{base})]$ and Longitudinal systolic function reserve index =
 631 $\Delta S' [1 - (1/ S'_{base})]$. Patients with an absolute increase in $\Delta E' [1 - (1/ E'_{base})] = \text{cm/s}$ or $\Delta S' [1 - (1/$
 632 $S'_{base})]$ cm/s of 0.7 cm/s, i.e., a 15 % in relative increase in cm/s from an assumed mean value
 633 of 6 cm/s [13,14]. This assumption is estimated in accordance with previous human data [3, 4].
 634 In that case we need to investigate 68 patients to demonstrate a mean absolute difference of 0.7
 635 cm/s with an alpha error of 5 % and a beta error of 80 %, in an open labelled parallel trial. This
 636 calculation is done with a standard deviation for the method assumed to be 1.0 cm/s (absolute).
 637 We estimate that some subject will drop-out, therefore we will investigate 80 subjects (40 in
 638 each group). See attached figures. These figures (A and B), below.

639 *A) With the proposed sample size of 34 and 34 for the two groups, the study will have power of 81.2% to*
 640 *yield a statistically significant result. This computation assumes that the mean difference is -0.7*
 641 *(corresponding to means of 6.0 versus 6.7) and the common within-group standard deviation is 1.0.*

Alpha = 0.050, Tails = 2, Mean 1 = 6.000, Mean 2 = 6.700

[figure not shown]
642

Protocol No: EudraCT nr 2010022695-31

Date: 20110204

Version: 7.5

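### The primary endpoint in section 3.1 is worded as a responder criterion, but the 81.2% power in section 9.2 is for a difference in means and does not apply to it

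*Protocol*

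**What the plan says.** Section 3.1 gives the primary endpoint as "Subjects achieving an absolute increase in left ventricle longitudinal function and/or functional", continuing "reserve during rest and/or after exercise of 0.7 cm/s, i.e". The unit is the subject and 0.7 cm/s is a cut-off. The criterion is also an and/or composite: function or reserve, rest or exercise, E' or S'.

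Section 9.2 first describes the endpoint as an improvement in longitudinal contraction, then repeats the patient-level 0.7 cm/s threshold. The calculation that follows is of another kind: "In that case we need to investigate 68 patients to demonstrate a mean absolute difference of 0.7" cm/s. Its inputs are "Alpha = 0.050, Tails = 2, Mean 1 = 6.000, Mean 2 = 6.700", and on the spread, "calculation is done with a standard deviation for the method assumed to be 1.0 cm/s (absolute"). The result is "With the proposed sample size of 34 and 34 for the two groups, the study will have power of 81.2% to" reach significance. Recruitment is raised to 80 (40 per arm) for drop-out, while section 2.1 expects 80 to complete.

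The Protocol Summary has a third form with no threshold: "Increase in left ventricle longitudinal function and/or functional reserve during rest and after exercise".

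Nowhere does the protocol give a responder rate, an SD of individual change, or a power for comparing proportions.

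**The concern.** The figure 0.7 cm/s does two jobs. In section 3.1 it is the gain that one patient must reach to count; in the power calculation it is the distance between two group means. These define different endpoints, with different analyses and different power. Splitting patients at a cut-off discards information on how far each one moved, so on a given measure a comparison of proportions usually needs more patients than a comparison of means.

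Two things are at stake. If section 3.1 is followed literally, the stated power has no support. And while both readings stand, the choice between mean change and responder proportion stays open until the data are in. Endpoint definition and sample-size justification are both fixed in the protocol, so a separate analysis plan could not follow one of these passages without departing from the other.

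**Working it through.** **Inputs from section 9.2.** Two-sided alpha 0.05; means 6.0 and 6.7 cm/s; SD 1.0 cm/s; 34 evaluable per arm, 40 recruited per arm. The text writes "cm/s with an alpha error of 5 % and a beta error of 80 %, in an open labelled parallel trial"; I read the second percentage as 80% power, which agrees with the 81.2%.

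**Step 1: the plan's figure.** Two-sample t-test, noncentrality = 0.7 / (1.0 × √(2/34)) = 0.7 / 0.2425 = 2.886, on 66 degrees of freedom. Power is 81.2%, as stated. At 40 per arm it is 87.1%. The figure is therefore a comparison of means.

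**Step 2: a responder version, with assumptions.** The protocol does not state what is needed, so I assume (a) one measure, (b) normally distributed changes with mean 0 on glimepiride and 0.7 on liraglutide, and (c) an SD of individual change of 1.0. Then
- glimepiride: P(change ≥ 0.7) = 1 − Φ(0.7) = 24.2%
- liraglutide: P(change ≥ 0.7) = 1 − Φ(0) = 50.0%

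Power for 24.2% versus 50.0%, two-sided 5%:

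| Test | 34 per arm | 40 per arm |
|---|---|---|
| Fisher, exact enumeration | 52.3% | 59.0% |
| Normal approximation | 59.9% | 67.2% |
| Uncorrected chi-square, exact enumeration | 62.1% | 67.7% |

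For 80% power, with mean proportion (0.242 + 0.5)/2 = 0.371:
n = [1.96 × √(2 × 0.371 × 0.629) + 0.842 × √(0.242 × 0.758 + 0.25)]² / 0.258² = (1.339 + 0.554)² / 0.0666 ≈ 54 per arm (62 with continuity correction).

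**Step 3: how far the assumptions matter.** Section 9.2 pairs its SD with group levels (6.0 and 6.7), not changes. If 1.0 is the SD of levels at each visit, the SD of change is 1.0 × √(2(1 − r)) for a between-visit correlation r: 1.0 at r = 0.5, and 1.41 at r = 0. The table lets the glimepiride mean change run from −0.3 to +0.5, with liraglutide 0.7 higher, at 34 per arm; responder power is by normal approximation.

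| SD of change | Responder power | t-test on the same changes |
|---|---|---|
| 0.8 | 69-81% | 94.5% |
| 1.0 | 55-62% | 81.2% |
| 1.2 | 43-47% | 65.9% |
| 1.41 | 34-36% | 52.1% |

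On a single measure the responder comparison has less power than the t-test in every row.

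**Step 4: the composite in section 3.1.** With two or four components, an assumed correlation of 0 to 0.7 between them, SD of change 1.0 and no glimepiride change, power at 34 per arm (Fisher to uncorrected chi-square) is about 56-84% if every component improves by 0.7 cm/s, and about 12-46% if only one or half of them do. The document gives nothing to choose between these cases.

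**The case against.** The strongest reply is that a mean difference was intended throughout. The summary has no threshold, section 9.2 opens with an improvement and then speaks of a mean difference, and the protocol never mentions a proportion or a test of proportions. On that reading 81.2% stands and section 3.1 is only loosely worded. This reply has real support, and it is why the point is a mismatch to be resolved and not a demonstrated loss of power. It does not remove the mismatch: section 3.1 is where the primary endpoint is defined, and section 9.2 itself repeats the patient-level threshold.

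A reader might go the other way and infer that the endpoint as written has only about 52-62% power. The documents do not support that. The range describes a simplified single-measure endpoint under three unstated assumptions, and its width reflects only the choice between Fisher and chi-square, not uncertainty in the inputs. It also takes 34 per arm, although section 2.1 expects all 80 to complete, which gives 59-68%. For the actual composite, power could be well below that range or, in the most favourable case examined, slightly above 81.2%.

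**Conclusion.** The mismatch is certain: the sample size and the 81.2% belong to a comparison of means, and section 3.1 words the endpoint as a responder criterion. The stated power therefore does not apply to that endpoint as worded.

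The size of any loss is conditional. Under the three assumptions of Step 2, a true 0.7 cm/s effect would be missed about 38-48% of the time at 34 per arm (100 − 62 and 100 − 52), against about 19% for the comparison of means. Other plausible SDs of change move responder power from about 34-36% to 69-81%. It does not follow that the trial is underpowered, since that depends on which endpoint is meant.

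**What to change.** State one primary endpoint, in the same words, in the summary, section 3.1 and section 9.2: the between-arm difference in mean change from Visit 2 to Visit 5 in one named velocity or index. An analysis adjusted for the Visit 2 value is preferable. Report the proportion gaining at least 0.7 cm/s as supportive. The existing calculation then fits, provided the SD of 1.0 cm/s applies to the named measure; section 9.2 should say whether it is the SD of levels or of changes.

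If the responder endpoint is kept as primary, withdraw the 81.2% and restate the power for a comparison of proportions, giving the assumed responder rate in each arm and the exact definition of a responder. The 52-62% should not be written into the protocol as that power, because it rests on assumptions the sponsor has not made.

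The main option costs wording in three places. It needs no extra patients or measurements, since the schedule already has tissue Doppler echocardiography at Visits 2 and 5. The small downside is that the responder proportion is no longer the headline result.

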146 3.2 Secondary Endpoints

147 The changes from baseline for 18 weeks of liraglutide + metformin compared with glimepiride +
148 metformin treatment will improve or affect;

- 149 • Global LV function (echocardiography) expressed as ejection fraction (EF)
- 150 • Exercise ECG, including working capacity
- 151 • 24-hour blood pressure
- 152 • Energy delivering from the carotid artery
- 153 • N-terminal pro b-type natriuretic peptide (NT-proBNP) levels in serum over time and
- 154 symptoms of dyspnea or fatigue as assessed by patient and clinician using established
- 155 scoring systems.
- 156 • Gene expression (Affymetrix)
- 157 • Plasma markers of inflammation *i.e.* hsCRP, IL-6, TNF- α and PAI-1
- 158 • Plasma markers of endothelial activation *i.e.* E-selectin, VCAM-1, ICAM-1 and plasma
- 159 levels of nitrate/nitrite
- 160 • Lipids
- 161 • HbA_{1c}
- 162 • Body weight
- 163 • Adverse events in terms of hypoglycaemia
- 164 • Quality of life (SF 36)
- 165 • Blood test (venipuncture)

166 4 Design

167 4.1 Outline

168 The present trial is a two centre, open, assessor-blinded and active-controlled, parallel-group
169 trial, in combination with metformin. The trial will compare the treatment with liraglutide 1.8 mg
170 (s.c) QD + metformin up to 1 g BID, with that of glimepiride 4 mg QD (comparator) +
171 metformin up to 1 g BID, on LV function in subjects with type 2 diabetes.

172 Patients are asked to participate in the study and after informed and written consent has been
173 obtained, subjects will be screened based on the inclusion and exclusion criteria. If needed,
174 subjects will have metformin up-titrated to a maximal daily dose of 2g, or the highest tolerated
175 dose in the run-in period. Total trial duration for the individual subject will be 18 ± 4 weeks. A
176 population of 80 type 2 diabetic subjects will be investigated (Figure 1).

[figure not shown]
Protocol No: EudraCT nr 2010022695-31

Date: 20110204

Version: 7.5

10(30)

Fig 1.

177

178 4.2 Assessments and Procedures

179 The subjects will attend a screening visit (Visit 1) in order to assess their eligibility. If found
 180 eligible, the subjects will return at Visit 2 within approximately 4 weeks, after Visit 1, with an
 181 up-titration with metformin 1 g BID or the maximal tolerated dosage of metformin (Run-in
 182 period).

183 At Visit 2 patients will be tested for;

- 184 • Heart function at rest and during an exercise ECG Stress Test with tissue Doppler

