258 degree atrioventricular block.
259 11. Implanted pacemaker.
260 12. Supine systolic blood pressure <85 mm Hg or >200 mm Hg.
261 13. Primary renal impairment (creatinine clearance < 30 ml/min), or creatinine clearance $<$
262 60 ml/min if treated with metformin.
263 14. Uncorrected hypokalemia or hyperkalemia (potassium <3.5 mmol/l or >5.5 mmol/l).
264 15. Significant anemia (Hb < 90 g/l)
265 16. Treatment with another investigational agent within 30 days before study entry, judged
266 by the investigator.
267 17. Severe gastrointestinal disease, including gastroparesis. As judged by the investigator.
268 18. Body mass index (BMI) > 40 kg/ m^2 .
269 19. Malignant neoplasm requiring chemotherapy, surgery, radiation or palliative therapy in
270 the previous 5 years. Patients with intraepithelial squamous cell carcinoma of the skin
271 treated with topical 5FU and subjects with basal cell skin cancer are allowed to enter the
272 trial.
273 20. Females of child bearing potential who are pregnant, breast-feeding or intend to become
274 pregnant or are not using adequate contraceptive methods (adequate contraceptive
275 measures as required by local law or practice).
276 21. Current drug and alcohol abuse.
277 22. History of acute or chronic pancreatitis
278 23. Subjects considered by the investigator to be unsuitable for the study.

279 **5.3 Criteria for Withdrawal**

280 The subjects may withdraw at will at any time. The subjects may be withdrawn from the trial at
281 the discretion of the Investigator due to safety concerns or if judged non-compliant with trial
282 procedures. Subjects randomised in error must be withdrawn from the trial

283 A subject must be withdrawn if the following applies:

- 284 1. Pregnancy or intention of becoming pregnant
- 285 2. Participation in other trials throughout the trial
- 286 3. Serious heart failure or a cardiovascular event

287 **5.4 Subject Log**

288 All subjects in the screening process will be documented in a medical chart accordingly to their
289 inclusion criteria or exclusion criteria.

290 **6 Treatment**

291 All subjects have been instructed to up-titrate metformin to 1 g BID, or maximal tolerated dose
292 of metformin, before randomisation (run-in period). At randomisation (Visit 2) subjects will be
293 randomised into one of the two treatment groups; liraglutide 1.8 mg (s.c) QD (initial dose of 0.6
294 mg with an up-titration of 0.6 mg every week, final dose 1.8 mg) or glimepiride 4 mg (p.o) QD

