295 (initial dose of 2 mg, with an up-titration of 1 mg every week, final dose 4 mg), both in
296 combination with metformin 1 g BID.

297 Subjects will be instructed to take metformin meanwhile the breakfast and the dinner meal.

298 Subjects will be instructed to take glimepiride before the breakfast meal and liraglutide at the
299 same time point every day.

300 **6.1 Description of Investigational Medicinal Products**

301 Liraglutide will be available as a solution for injection at a concentration of 6.0 mg/ml, supplied
302 in a 3 mL pre-filled disposable pen.

303 Glimepiride will be available as tablet for oral administration, each tablet containing 1 mg, 2 mg
304 or 4 mg of glimepiride.

305 **6.2 Packaging, Labelling, Storage and Handling of Investigational Medicinal Products**

306 The trial products will be packed and labelled by an external clinical supply contractor, which
307 can be done since both trial products are commercially available. Labelling will be in accordance
308 with Annex 13, local law and trial requirements.

309 Each investigator site will be supplied with sufficient trial products for the trial.

310 Trial product will be packed in dispensing units and will be distributed to the sites according to
311 enrolment and randomisation.

312 The trial products will be dispensed to each subject at Visit 2, as required according to treatment
313 group. The randomisation procedure will allocate trial product Dispensing Unit Number (DUN)
314 to the subject at the dispensing visit. The correct DUN must be dispensed to the subject at the
315 dispensing visit.

316 Instruction to the subject on how to use the trial liraglutide pre-filled disposable pen should be
317 provide by the Investigator at Visit 2.

318 The trial products should be stored in accordance with the storage conditions as stated in the
319 Summary of Product Characteristics for each product, see Appendices 17.2 and 17.3.

320 The Investigator must ensure availability of proper storage conditions, and record and evaluate
321 the temperature (at least every working day). Storage facilities should be checked frequently. A
322 log to document the temperature must be kept.

323 Storage and in-use conditions:

324 Liraglutide

325 Not in use: The liraglutide pre-filled pen must be stored in a refrigerator at a temperature between
326 +2°C and + 8°C. Keep away from the cooling element. Do not freeze and do not use if it has
327 been frozen.

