328 In-use: After first opening the liraglutide pre-filled pen can be stored for one month at
329 temperatures below +30°C or in a refrigerator between +2°C and +8°C.

330 Do not freeze and do not use if it has been frozen.

331 The pen must be protected from all sources of light, and the pen cap should be kept on when the
332 pen is not in use. The liraglutide should not be used if it does not appear clear and colourless.

333 Glimepiride

334 Store at temperatures below +30°C. Store in original package. Sensitive to damp.

335 In case of incorrect storage, the site staff should inform the Principal Investigator without delay.
336 The trial products must be set on-hold until notified by Principal Investigator.

337 No trial product should be dispensed to any person not enrolled in the trial.

338 **6.3 Treatment Assignment**

339 The study is an open, assessor-blinded and active-controlled, parallel-group trial.

340 Randomisation will be carried out in a (1:1) manner using an interactive voice/web response
341 system (IV/WRS) to randomise subjects into the treatment groups:

- 342 • Liraglutide QD or
- 343 • Glimepiride QD

344 both in combination with metformin.

345 **6.4 Concomitant Medication**

346 Type 2 diabetic patients with metformin, as a single oral anti-diabetic drug, or diet controlled,
347 will be eligible for the study.

348 All other new medications in the study period will be documented in the CRF.

349 **6.5 Compliance to Treatment**

350 Subject compliance will be assessed by monitoring of drug accountability. The unused amount of
351 trial product will be assessed against the dispensed amount and, in case of discrepancies, the
352 subjects must be asked.

353 **6.6 Product Accountability and Destruction**

354 The person delegated by the Investigator must keep track of all received, used, partly used and
355 unused trial products, and if possible all empty packaging, This shall be properly documented.

356 Used, partly used and unused trial products and empty packaging must be stored separately from
357 non-allocated trial products. Used, partly used and unused trial products must be stored until the
358 monitor has performed drug accountability.

359 The monitor is responsible for arranging destruction of trial products. The destruction will be
360 performed in accordance with local legislation and recorded on a destruction form.

361 **6.7 Continuation of Treatment**

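### Every subject is to take metformin, yet exclusion 13 makes its 60 ml/min limit conditional on metformin treatment, so the renal limit for diet-controlled patients is unclear

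*Protocol*

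**What the plan says.** **Metformin for all.** Section 6 states: "All subjects have been instructed to up-titrate metformin to 1 g BID, or maximal tolerated dose", and places this before randomisation. Section 4.2 puts it between Visit 1 and Visit 2, as an "up-titration with metformin 1 g BID or the maximal tolerated dosage of metformin (Run-in" period). After randomisation both arms are given in "combination with metformin 1 g BID" (section 6). Section 4.1 caps the daily dose at 2 g and allows the highest tolerated dose instead.

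**Who may enter.** Section 6.4 describes the eligible background treatment: "Type 2 diabetic patients with metformin, as a single oral anti-diabetic drug, or diet controlled". A diet-controlled patient takes no metformin at screening.

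**When eligibility is judged.** Section 4.2: "The subjects will attend a screening visit (Visit 1) in order to assess their eligibility. If found" eligible, the subject returns for Visit 2 after the run-in.

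**The renal criterion.** Exclusion 13 in section 5.2 has two tiers. It begins "Primary renal impairment (creatinine clearance < 30 ml/min), or creatinine clearance" and goes on to set the second tier at below "60 ml/min if treated with metformin".

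**Scheduled bloods.** Creatinine is in the section 7.3 safety list without a visit of its own. The Schedule of Investigational Events ticks blood chemistry at Visits 2 and 5 only, and section 4.2 lists the blood test at the same two visits. The Visit 1 column has ticks for consent, the inclusion/exclusion criteria and a pregnancy test.

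**The concern.** A two-tier renal limit makes sense in a trial where some subjects take metformin and others do not. Here the design gives it to everyone, so the condition attached to the 60 ml/min tier should either always be met or not be there. Because eligibility is judged while diet-controlled patients are still off metformin, an investigator who applies the criterion as written at Visit 1 may conclude that only the 30 ml/min tier concerns them. The run-in then starts the drug on which the stricter limit depends.

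Two things are at stake. Some subjects could be started on metformin at a clearance the protocol itself names as disqualifying with that drug. And the two centres could apply different renal limits to the same kind of patient.

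**Working it through.** The plan gives no figure to reproduce on this point; the check is of eligibility logic and visit timing.

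**Step 1: is metformin really universal?** Section 6 says all subjects, and both arms include it. Section 4.1 qualifies the up-titration: "subjects will be screened based on the inclusion and exclusion criteria. If needed", metformin is raised to 2 g daily or the highest tolerated dose. That qualifier can spare someone already at the target dose. It cannot spare a diet-controlled patient, who takes none. No metformin-free path is described.

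**Step 2: exclusion 13 under its two readings.** Let C be creatinine clearance in ml/min.

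- Reading (a), metformin use as it stands at Visit 1: exclude if C < 30, or if C < 60 and the patient already takes metformin.
- Reading (b), metformin taken or about to be taken in the trial: exclude if C < 30, or if C < 60 and the patient takes or will take metformin. The last condition is met by everyone on the protocol's regimen.

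| C (ml/min) | (a) diet-controlled | (a) on metformin | (b) either | Single limit C < 60 |
|---|---|---|---|---|
| 25 | excluded | excluded | excluded | excluded |
| 29 | excluded | excluded | excluded | excluded |
| 30 | **admitted** | excluded | excluded | excluded |
| 45 | **admitted** | excluded | excluded | excluded |
| 59 | **admitted** | excluded | excluded | excluded |
| 60 | admitted | admitted | admitted | admitted |
| 75 | admitted | admitted | admitted | admitted |

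The readings differ only for diet-controlled patients with C of at least 30 and below 60. Under (b) the outcome equals the single limit at every value, so the 30 ml/min tier excludes nobody further. The one exception would be a subject who tolerates no metformin at all, for whom only the 30 ml/min tier would apply.

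**Step 3: dose reached under reading (a).** The target is 1 g twice daily: 2 × 1 g = 2 g a day.

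**Step 4: timing.** Visit 1 falls at week -4 to -1 and Visit 2 at week 0, so the run-in lasts 1 to 4 weeks. The first ticked blood chemistry (Visit 2) comes after it.

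**Step 5: is the schedule gap peculiar to creatinine?** Sections 5.1 and 5.2 set four numeric laboratory limits: HbA1c (inclusion 3), creatinine clearance (exclusion 13), potassium (exclusion 14) and haemoglobin (exclusion 15). The schedule ticks a Visit 1 sample for 0 of the 4. The echocardiogram needed for inclusion 2 has no Visit 1 tick either. The chart therefore does not itemise what lies behind its eligibility tick for any of them.

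**Step 6: effect on the inference.** The sample size in section 9.2 rests on a difference of 0.7 cm/s, an SD of 1.0 cm/s and 34 per group. None of these depends on exclusion 13, and metformin is common to both arms.

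**The case against.** **Reading (b) may be the more natural one.** Every description of the arms includes metformin, and where the protocol means earlier treatment it says so (exclusions 3 to 5); exclusion 13 does not. On that reading nobody at 30-59 ml/min enters, and the fault is redundant wording. This carries weight: the documents do not show that the authors meant to admit such patients. But only reading (a) gives the 30 ml/min tier ordinary work to do, so the text supports neither reading firmly.

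**The 30 ml/min tier is not wholly without function.** A fully metformin-intolerant subject would fall under it. That is right as logic, though the protocol describes no such subject, and intolerance is normally learned by taking the drug.

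**Safeguards exist.** Exclusion 23 lets the investigator exclude unsuitable subjects, section 5.3 allows withdrawal for safety, and blood is drawn at Visit 2, listed before randomisation. These reduce the practical consequence. They do not correct the rule, and the Visit 2 sample follows the run-in.

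**A reader might infer from the schedule that metformin is started with renal function unknown.** The documents do not support this. Section 4.2 makes the run-in conditional on eligibility, and the Visit 1 tick for the inclusion and exclusion criteria implies that a clearance value is already at hand, for example from the patient's records. Step 5 shows that leaving out the underlying tests is how the chart is drawn. What stands is small: neither the source of the value nor its being seen before dosing is stated.

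**Conclusion.** The point holds for the wording of exclusion 13. Its conditional 60 ml/min limit does not fit a design in which all subjects are to take metformin and diet-controlled patients may enter. The disputed group is diet-controlled patients at 30-59 ml/min: admitted and started on up to 2 g a day under the literal reading, excluded under the other.

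How many subjects this would be cannot be derived, because the protocol gives neither the diet-controlled share nor the distribution of clearance. Divergence between the two centres is likewise a possibility the wording leaves open; nothing in the document shows that it occurred.

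The conclusion assumes that eligibility is settled at Visit 1, as section 4.2 says, and that no metformin-free path exists, since none is described. It uses only the protocol's own 60 ml/min limit and no outside threshold. A reader might go further and see a threat to the treatment comparison; there is none here, neither a loss of power nor a bias between arms. The matter is one of safety and uniform eligibility. It should be corrected because the correction is cheap. The missing Visit 1 creatinine is a minor remark beside it.

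**What to change.** Reword exclusion 13 as a single limit, creatinine clearance < 60 ml/min, for all subjects, and delete the 30 ml/min tier. This excludes the same people as reading (b) and, compared with reading (a), additionally excludes diet-controlled patients at 30-59 ml/min.

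As a minor addition, show a creatinine value (a recent chart value or a Visit 1 sample) in the Visit 1 column of the schedule, and state that it must be seen before metformin is started or raised. The other laboratory limits could be itemised in the same edit, but creatinine comes first because the run-in drug depends on it.

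The cost is one reworded criterion and one value at a visit already planned. Eligibility becomes slightly narrower than under the literal reading and is unchanged under the other. No visit is added and the sample size stays as it is.
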